Traditionally, phase 2 EEU studies have been utilized to confirm dose selection and test efficacy of anti-allergic therapies (Biedermann, 2019b) (Couroux, 2009) (Didier, 2011) (Horak, 2009) (Nolte, 2016) (Nolte, 2015). Field studies can have large geographic variability in pollen exposures compounded by the limited ability to predict local seasonal and climate changes (Zhang, 2022) in addition to individual differences in exposures. Data indicate that the magnitude of treatment effect is impacted by degree of pollen exposures (Durham, 2014), which highlight the challenges in field studies. The current COVID-19 pandemic has also imposed several challenges and restrictions in activities, as well as mask mandates in recent times that have complicated field assessments of symptoms in the short term (Bergmann, 2021). Alternatively, field studies may be integrated into EEU studies as "hybrid" trials, to potentially demonstrate clinical efficacy for novel therapies with fewer participants with shorter timelines, but more importantly, allowing the interpretation of efficacy in both controlled allergen exposures, as well as real-world field-based assessments (Ellis, 2021a). To support a goal to use EEU studies as an adjunct to field studies, investigators have published data demonstrating that there is a high correlation between allergic symptoms elicited in the EEU and in the field (Jacobs, 2011) (Jacobs, 2014), that EEUs can be performed both in season and out-of-season (Badorrek, 2011) (Ellis, 2021b), and that 2 EEUs can be used together in dual-center clinical trials (Ellis, 2019), in addition to assessing different allergens sequentially in EEU trials (Couroux, 2019).

Furthermore, testing of REGN5713-5714-5715, REGN5713-5715, and REGN5715 out-of-season and in-season, both in chamber and field settings, provides a comprehensive approach to the evaluation of these anti-Bet v 1 antibodies.

Skin Prick Test Endpoints Support the Evaluation of the Anti-Bet v 1 Antibodies

Development of allergen-specific polyclonal IgE antibodies is considered a hallmark of allergen "sensitization" (Flicker, 2003) (Murphy, 2017). A larger wheal size showing a greater degree of sensitization significantly increases the risk of having symptoms. This has also been demonstrated specifically for birch allergen (Haahtela, 2014) suggesting the relevance of the SPT wheal size in predicting clinical allergy with the likelihood of developing symptoms.

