demonstrate that the participant has moderate to severe rhinitis symptoms during a birch pollen exposure. Participants will be asked to refrain from taking specific prohibited medications (Section 7.9.1) within the specified period preceding screening and EEU visits.

- Screening baseline assessment: Eligible participants who meet eligibility criteria for the study (including screening birch EEU challenge requirement) will record daily symptom and medication scores for approximately 2 weeks or longer (at minimum 1 week) until randomization
- Screening EEU challenges and baseline symptom and medication assessment are recommended to be done outside of relevant pollen seasons for pollen-allergic participants.
- Participants who are sensitized to oak and meet eligibility criteria for the study (including screening birch EEU challenge requirement) will also undergo an EEU challenge with oak allergen (visit 3) to determine clinical allergy to oak during screening.
- **Re-screening**: Participants may be re-screened up to one time; however, rescreening is not permitted if a participant screen failed on birch sensitization criteria (birch SPT or sIgE to birch or sIgE to Bet v 1) or screening birch EEU challenge eligibility criteria.

Randomization and study drug dosing (dose #1): Participants who meet all inclusion but no exclusion criteria will undergo randomization at visit 4. Stratification factors at randomization include oak allergy, grass sensitization status, and EEU site. Randomization and treatment assignment for Part A is discussed in Section 7.5. Participants will be observed for 2 hours after receiving the SC dose of study drug.

A primary analysis will be performed after all participants complete at least day 29 EEU challenges or discontinue.

Follow-up period after EEU exposures until visit 10.

Part B Study Periods:

As outlined above in Figure 1, study Part B consists of an on-treatment efficacy assessment period, an off-treatment safety follow-up period, and the end-of-study visit. These study periods are described below.

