6.2. Study Population

6.2.1. Inclusion Criteria

A subject must meet the following criteria to be eligible for inclusion in the study:

- 1. Generally healthy males and females, age 18 years or older at the time of screening.
- 2. Documented or subject-reported history of birch tree pollen-triggered allergic rhinitis symptoms with or without conjunctivitis (for at least 2 seasons)
- 3. Positive SPT with birch tree pollen extract (mean wheal diameter at least 5 mm greater than the negative control) in screening period
- 4. Positive sIgE tests for birch tree pollen and Bet v 1 (≥0.7 kUa/L) in screening period
- 5. Demonstrated TNSS ≥6 out of 12 on at least 2 time points during the birch EEU exposure challenge in screening period
- 6. Willing and able to comply with clinic visits and study-related procedures
- 7. Provide informed consent signed by study participant or legally acceptable representative
- 8. Able to understand and complete study-related questionnaires

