- 7. Part A EEU challenges: TNSS and TOSS are recorded using an e-diary at baseline and then every ~20 minutes while in the EEU, then continued ~ every 2 hours until ~24 hours after the start of the EEU exposure (except during sleep). After completion of the EEU challenges, use of allergy medicines will be recorded in the e-diary until ~24 hours after the start of the EEU challenges. An assessment of TNSS is performed once prior to the start of the EEU exposure at visits 2, 3, 6, 7, 8, 9. If TNSS ≤2, then the visit activities can proceed. If TNSS is >2, then the visit can be rescheduled within the window. Washouts for medications prior to EEU visits are specified in prohibited medications (Section 7.9.1).
- 8. Part B EEU challenges: There are no TNSS thresholds for the peak birch pollen season EEU visit (visit 13). The birch EEU challenge at the end of the season (visit 14) may not be performed in grass-allergic participants who are highly symptomatic or unable to wash out allergy relieving rescue medications due to grass pollen allergy symptoms, per PI discretion.

- 9. On a case-by-case basis, an EEU challenge visit window post-randomization may be extended up to +14 days for any illnesses (eg, respiratory illness, common cold, etc) that may potentially confound the assessments and/or potentially impact participant safety, per PI discretion in consultation with the sponsor.
- 10. Randomization may occur within 1 day prior to study drug administration.
- 11. In Part B, participants who received either 3-mAb, 2-mAb, 1-mAb, or placebo in Part A will continue the same treatment in Part B.
- 12. Dosing window for visit 11 is within approximately 0 to 3 weeks prior to start of the anticipated BPS.
- 13. Visit timeframes in Part B (visits 10 to 15) may vary based on the timing and duration of the anticipated BPS. End-of-season EEU challenge (visit 14) should occur after the end of the protocol-defined end of the BPS.
- 14. Dose #2 should be administered at minimum 12 weeks after dose #1.
- 15. Participants will be contacted within 1 day (visit 12) after dose 2 (visit 11) via telephone to monitor safety trends.

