7.2.2.1. Estimand Framework for Secondary Endpoints

The intercurrent events, strategies, and the corresponding missing data handling approaches for the secondary estimands of interest for the secondary endpoints are provided in detail in Table 3:

Table 3: Summary of Estimands for Secondary Endpoints

	Estimand			
Endpoint Category	Endpoint	Population	Intercurrent event(s) handling strategy and missing data handling	Population-level summary
Secondary endpoint - Continuous	Titrated SPT MWD	FAS ¹	If the antihistamines are not withheld before the titrated SPT, the post-randomized data will be assigned by worst observation (including baseline) before the collection of the assessment from the same participant (composite strategy). If all dilutions are missing due to any reason, e.g., early start of BPS, then the averaged value will be imputed using multiple imputation (MI).	ANCOVA model with treatment group and stratification factors as fixed effect and the baseline tSPT as a covariate.
	EEU symptom scores ³ in Part B	FAS-B	Same manner as the primary endpoint with the following exception: If systemic steroids, biologics or immune therapeutics impacting type 2 allergic disease are used due to birch pollen related symptoms ⁶ prior to the EEU challenge, data will be set to mean score from 2 to 6 hours in the baseline EEU (BOCF, composite strategy).	Same manner as the primary endpoint
	Field symptom scores ⁴ in BPS ⁵ and peak BPS	FAS-B	 The intercurrent events will be handled as follows: If Systemic steroids, Biologics or immune therapeutics impacting type 2 allergic disease are used due to birch pollen related symptoms⁶, data will be set to mean score from the other participants in the same treatment group (composite strategy). If due to any other reason, data after the use of medication will be set to missing (hypothetical strategy). Study provided anti-allergy rescue treatment taken during the study: all available data will be utilized (treatment policy) Data during travel periods with no exposure to birch pollen will be set to missing and other observed data during exposure to birch pollen will be used to calculate the mean scores (while on treatment policy) 	ANCOVA model with treatment group, stratification factors as fixed effect, average pollen count during local BPS and the corresponding pre-treatment baseline symptom scores as covariate.

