10.7. Biomarker Data

Exploratory biomarker data may be described in a separate exploratory analysis plan. Analyses may include (but are not limited to) evaluating relationships between biomarkers and clinical responses. Exploratory biomarker variables may include (but are not limited to) serum allergenspecific IgE levels (birch, Bet v 1, Bet v 2, and other common allergens) and basophil activation. Relevant biomarker data analyses may be included in the CSR and/or a separate biomarker report.

11. **DATA CONVENTIONS**

11.1. **Definition of Baseline for Efficacy/Safety Variables**

Unless otherwise specified, the Baseline assessment for all measurements will be the latest available valid measurement taken prior to the administration of investigational product. The following rules specify the determination of baseline by both date/time information:

• The date and time of first injection will be used to determine the baseline for the AE, lab, PK and ADA data.

Date: May 31, 2023

• Only the date of first injection will be used to determine the baseline for other data except the AE, lab, PK and ADA data.

For the efficacy endpoints, the baseline is defined as following:

- For all symptom scores (TNSS or TOSS) collected in EEU chambers, the baseline is defined as the mean of the corresponding measurements (2 to 6 hours) during the allergen EEU challenge in screening period. The baseline visit for Birch is Visit 2, and the baseline visit for Oak is Visit 3.
- For daily e-diary scores (daily TNSS, daily TOSS, DMS, daily TSS, daily CSMS, RQLQ(S), PFASQ, and outdoor questionnaire), there are two baselines defined, pretreatment baseline and pre-season baseline.
 - The pre-treatment baseline is defined as the average of the daily score during the screening period before the first dose. All days with scores during the screening period will be used to calculate the average, except for the day of and one day following EEU challenge.
 - The pre-season baseline is defined as the average of the daily score start from the Visit 10 to the day before the local BPS, except for the day of and one day following EEU challenge.

The number of non-missing daily records must be at least 3 after excluding the records happening on the same day and the next day of the EEU visit for pre-treatment and preseason baseline (both pre-treatment baseline) calculation. If the baseline value is smaller than 1, the baseline will be set to 1.

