14. APPENDIX

14.1. Summary of Statistical Analyses

Efficacy/PD Analysis:

Endpoint	Analysis Populations	Primary Analysis	Statistical Method	Supportive Analysis	Subgroup Analysis	Other Analyses
Primary E	ndpoint					
EEU TNSS (2- 6 hours)	FAS	Mean at day 29 for 3-mAb versus placebo	ANCOVA model with treatment group and stratification factors as fixed effect and the baseline mean TNSS (2 to 6 hours) at visit 2 as a covariate.	Yes, sensitivity and supplemental analysis described in Section 7.2.1.2	Yes, subgroups are listed in Section 7.2 .1.3	Plots
Secondary	Endpoints					
EEU (2-6 hours): TNSS, TOSS, TSS	FAS	Mean, change and percent change from pre-treatment baseline, at days 29*, 57, 85 for each of anti-bet v 1 monoclonal antibodies versus placebo	Same as above	No	No	Numerical comparison between three anti-bet v 1 monoclonal antibodies.
EEU (2-6 hours): TNSS, TOSS, TSS	FAS with subjects allergic to oak	Mean, change and percent change from pre-treatment baseline, at days 36 for each of anti-bet v 1 monoclonal antibodies versus placebo	Same as above	No	No	Comparison between combined active group versus placebo
EEU (2-6 hours): TNSS, TOSS,	FAS - B	Mean for each of anti-bet v 1 monoclonal antibodies versus placebo	Same as above	No	No	No
CSMS, TSS, TNSS, TOSS, DMS	FAS - B	Mean, change and percent change from pre-treatment and pre-season baseline, in BPS, peak BPS for each of anti-bet v 1 monoclonal antibodies versus placebo	Same as above except for the average pollen count during local BPS will also be used as a covariate in the model.	No	No	Analyses using 30 grains/ m³ as the cutoff for defining BPS start and end

Endpoint	Analysis Populations	Primary Analysis	Statistical Method	Supportive Analysis	Subgroup Analysis	Other Analyses
RQLQ(S)	FAS - B	Mean, change and percent change from pre-treatment and pre-season baseline, in BPS, peak BPS for each of anti-bet v 1 monoclonal antibodies versus placebo	Same as above	No	No	No
Titrated SPT MWD AUC	FAS for Day 29, 57, and 85 FAS with visit 10 performed at least 12 weeks after dose #1 for Day 127	Change and percent change from pretreatment baseline, at days 29, 57, 85 and 127 for each of antibet v 1 monoclonal antibodies versus placebo	Same as above	No	No	Plots; Numerical comparison between three anti-Bet v 1 monoclonal antibodies.

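### The Part B field ANCOVA leaves out the visit 2 birch EEU score, a pre-randomization measure of birch reactivity already on file, so some precision may be lost

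*SAP*

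**What the plan says.** SAP Section 7.2.2.1, Table 3, models the field scores (CSMS, TSS, TNSS, TOSS, DMS) over the BPS and peak BPS with treatment, the stratification factors (oak allergy, grass sensitization, EEU site) and "average pollen count during local BPS and the corresponding pre-treatment baseline symptom scores as covariate".

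SAP Section 11.1 defines the diary baseline: "The pre-treatment baseline is defined as the average of the daily score during the screening period before the first dose". It adds a lower bound: "If the baseline value is smaller than 1, the baseline will be set to 1". On timing, Protocol Section 5.1 says: "Screening EEU challenges and baseline symptom and medication assessment are recommended to be done outside of relevant pollen seasons for pollen-allergic participants".

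Every eligible participant also has a birch chamber score from visit 2, because Protocol Section 6.2.1 requires: "Demonstrated TNSS ≥6 out of 12 on at least 2 time points during the birch EEU exposure challenge in screening period". SAP Table 2 uses the visit 2 mean TNSS as the covariate for the primary endpoint. Table 3 does not list it for the field scores.

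SAP Section 14.1 describes the field model as: "Same as above except for the average pollen count during local BPS will also be used as a covariate in the model". The RQLQ(S) row there refers back in the same way, and RQLQ(S) has no row in Table 3.

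In support of the hybrid design, Protocol Section 3.2.1 cites published data that "there is a high correlation between allergic symptoms elicited in the EEU and in the field".

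**The concern.** An ANCOVA gains precision from covariates that predict the outcome. The outcome here is symptom burden under birch pollen exposure. The diary baseline is meant to be recorded without that exposure, and its lower bound removes variation among participants with low scores. The visit 2 chamber mean records the response to birch pollen itself, is measured before randomization and is already in the database. The protocol's own rationale is that chamber and field symptoms go together, yet the field model does not draw on it.

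What is at stake is the width of the intervals for active arm versus placebo in the field. No power is stated for these endpoints. FAS-B excludes participants who do not receive dose #2, and SAP Section 2.2 already considers 50 participants per arm.

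**Working it through.** **The plan's own figures.** The documents give no sample size, SD or power for the field endpoints, so there is no field figure to reproduce. The Part A figures do reproduce. With a difference of 1.61, an SD of 2.8 and a two-sided 5% t-test, the noncentral t gives 65 per arm for 90% power and 81.2% power at 50 per arm; 65/(1 − 0.10) = 72.2, rounded up to 73. These say nothing about the field model.

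**Gain from adding the visit 2 score.** Let r be the partial correlation of the visit 2 mean with the seasonal mean, given the terms already in the model. Residual variance is multiplied by 1 − r² and the standard error by √(1 − r²). The equivalent sample size is multiplied by 1/(1 − r²). A comparison with 80% power moves to Φ((1.960 + 0.842)/√(1 − r²) − 1.960). The 80% is illustrative, and r is assumed over 0.1 to 0.6 because no coefficient is given.

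| Assumed r | SE ratio | SE reduction | Worth this many more participants | Power, from 80% |
|---|---|---|---|---|
| 0.1 | 0.995 | 0.5% | 1% | 80.4% |
| 0.2 | 0.980 | 2.0% | 4% | 81.6% |
| 0.3 | 0.954 | 4.6% | 10% | 83.6% |
| 0.4 | 0.917 | 8.3% | 19% | 86.4% |
| 0.5 | 0.866 | 13.4% | 33% | 89.9% |
| 0.6 | 0.800 | 20.0% | 56% | 93.8% |

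**Overlap with the diary baseline.** Let r1 be the correlation of diary with outcome, r2 that of chamber score with outcome, and r12 that between the two. With both in the model, R² = (r1² + r2² − 2·r1·r2·r12)/(1 − r12²).
- Assumed r1 = 0.4, r2 = 0.3, r12 = 0.5: R² = (0.16 + 0.09 − 0.12)/0.75 = 0.173. Residual variance goes from 0.840 to 0.827, and the SE falls by only 0.8%.
- Assumed r1 = 0.2, r2 = 0.5, r12 = 0.3: R² = (0.04 + 0.25 − 0.06)/0.91 = 0.253. Residual variance goes from 0.960 to 0.747, and the SE falls by about 12%.

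**Effect of the lower bound on the diary baseline.** No diary distribution is given, so this was simulated with exponential-shaped baselines and an underlying correlation of 0.4 with the outcome. Before the bound, the correlation on the diary scale is 0.36.

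| Assumed mean diary score | Share below 1 | Correlation after the bound |
|---|---|---|
| 0.3 | 96% | 0.14 |
| 0.6 | 81% | 0.24 |
| 1 | 63% | 0.30 |
| 3 | 28% | 0.35 |

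The bound matters a good deal if out-of-season scores are very low, and hardly at all if they average about 3.

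**Cost if the added term is useless.** One degree of freedom. For an assumed 150 to 200 participants analysed, the variance rises by roughly 1/150 to 1/200, that is 0.5% to 0.7%.

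**The case against.** The strongest objection is that adjusting for the same instrument's pre-randomization baseline, plus strata and pollen count, is standard and valid, so an extra covariate is a preference. The first part stands: nothing in Table 3 is invalid. But the proposed term is collected already, costs one degree of freedom and adds no bias, so the trade favours including it.

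Five stronger readings are tempting, and the documents do not support them.
- *The diary scores sit at the floor.* Out-of-season recording is recommended, not required, and no diary mean, SD or share below 1 is reported. The pre-exposure check at Part A chamber visits ("If TNSS ≤2, then the visit activities can proceed") is only an indirect sign. Nor is the diary tied to washouts as such: Protocol Section 7.9.1 attaches those to screening, EEU visits and skin testing, and rescue medication is dispensed at visits 2 and 3.
- *The diary is the only participant-level predictor in the model.* The strata are participant-level too. Oak allergy is defined by a chamber response, and SAP Section 7.2.1.3 calls grass sensitization more relevant to the field part. Both may take up some of what the visit 2 score would explain.
- *The cited high correlation guarantees a large gain.* It comes without a coefficient. It is also not the quantity needed, which is a partial correlation between one instantaneous screening score and a 24-hour reflective seasonal mean months later, mostly in treated participants with free access to rescue medication. The entry threshold also restricts the range of the chamber score.
- *Section 14.1 contradicts Table 3, or already includes the visit 2 score.* Followed literally, its back-references do lead to visit 2 TNSS. But they would put that score into the titrated SPT model too, where Table 3 names the SPT baseline. SAP Section 7.2.2 lets Table 3 override the primary method. This is loose wording to align, not a substantive conflict.
- *Formal conclusions or the ranking of active arms are at risk.* The field endpoints are outside the hierarchy in SAP Section 8.2, and Section 7.2 makes the active-arm comparisons numerical only.

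**Conclusion.** The point holds as an efficiency improvement, not as an error. Table 3 governs the field model and omits a pre-randomization measure of birch reactivity that every eligible participant has. Leaving it out biases nothing.

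The size is uncertain. It is negligible at a partial correlation of 0.2 or below (SE about 2% smaller at most) and can be under 1% when the score overlaps with the diary. It becomes material at 0.5 (about 13%). The entry rule of TNSS 6 or more makes the lower part of that range more likely. All these values rest on an assumed correlation, and the weakness of the diary baseline is inferred from its timing and lower bound. What is firm is the omission and its low cost; the gain is not.

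**What to change.** Before field data are unblinded, amend SAP Table 3 and Section 14.1 as follows.
- Add the visit 2 birch EEU mean (2 to 6 hours) as a covariate in the field ANCOVA, in addition to the pre-treatment diary baseline. Use TNSS for TNSS, TOSS for TOSS, and TSS for TSS and CSMS. For DMS and RQLQ(S), TSS is a reasonable choice, though the documents do not dictate one.
- State the same covariate list explicitly in both places instead of by back-reference, and cover RQLQ(S), which has no Table 3 row.
- Do not use the pre-season diary baseline as the substitute. It starts at visit 10, after dose #1, and treatment can affect it.

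The cost is SAP wording and one degree of freedom per model. No new data are needed.

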7.2.3. Analysis of Exploratory Endpoints

Continuous exploratory efficacy variables, e.g., change and percent change from pre-treatment baseline for TNSS, TOSS, TSS in birch pollen EEU challenges, will be analyzed by using an ANCOVA model similar to the analyses of primary endpoint. For categorical exploratory variables, only descriptive summary will be provided. In addition, the duration of the BPS and the average pollen counts will be provided by pollen site for Part B analysis.

Within-participants comparisons will be conducted using FAS and CS-A.

The combined active group is defined as participants who received any active treatment (REGN5713-5714-5715, REGN5713-5715, or REGN5715). For the oak allergen EEU challenge, the following endpoints will be analyzed by comparing the combined active group versus the placebo group:

- The mean of symptom scores (TNSS [2-6 hours], TOSS [2-6 hours] and TSS [2-6 hours]) during out-of-season oak allergen EEU challenge at day 36
- The change and percent change from pre-treatment baseline in symptom scores (TNSS [2-6 hours], TOSS [2-6 hours] and TSS [2-6 hours]) during an oak allergen EEU at day 36
- The change and percent change from pre-treatment baseline in the red oak titrated SPT mean wheal diameter (MWD) AUC

Rationale: REGN5715 is the only monoclonal antibody that has been demonstrated to exhibit binding to oak in pre-clinical ELISA experiments (REGN5713 and REGN5714 have not demonstrated binding). Therefore, symptom endpoints during day 36 oak EEU challenge and oak titrated SPT endpoints will be assessed in participants receiving active treatment (REGN5713-5714-5715, REGN5713-5715 or REGN5715) versus placebo (3:1) in subpopulation of oak allergic participants if the individual active arms versus placebo are reasonably comparable.

